### 6.6.2 Determination of drug concentration

Samples for determination of drug concentration in plasma will be analysed by the appointed bioanalytical laboratory on behalf of AstraZeneca. The laboratory will use a validated method of high performance liquid chromatography with tandem mass spectrometric detection (HPLC-MS/MS) after protein precipitation. The lower limit of quantification (LLOQ) of AZD5069 in plasma will be 1 nmol/L. Full details of the analytical method used will be described in a separate bioanalytical report.

Plasma samples from patients who were dosed with placebo will not be analysed for AZD5069.

Samples that are outside of the known stability of AZD5069 will not be reported.

Incurred sample reproducibility analysis, if any, will be performed alongside the bioanalysis of the test samples and reported in a separate bioanalytical report.

Any remaining plasma samples will be stored for possible further metabolism and pharmacokinetic investigations (Section 7.2.2). Any results from such analyses will be reported separately from the CSR.

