#### 5.4.2 Methods for unblinding the study

Individual treatment codes, indicating the treatment randomisation for each randomised patient, will be available to the investigator(s) or pharmacists from the IVRS/IWRS. Routines for this will be described in the IVRS/IWRS user manual that will be provided to each centre.

A copy of the randomisation scheme will also be made available to the PK bioanalyst, to enable the analysis of samples from patients who have received active treatment to be prioritised. This documentation will be placed in a secure location until the end of the study.

The treatment code should not be broken except in medical emergencies when the appropriate management of the patient requires knowledge of the treatment randomisation. The investigator documents and reports the action to AstraZeneca, without revealing the treatment given to the patient to the AstraZeneca staff.

AstraZeneca retains the right to break the code for SAEs that are unexpected and are suspected to be causally related to an investigational product and that potentially require expedited reporting to regulatory authorities. Treatment codes will not be broken for the planned analyses of data until all decisions on the evaluability of the data from each individual patient have been made and documented.

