## 5.5.2 Doses and treatment regimens

The investigational product will be taken orally twice daily, with doses approximately 12 hours apart (4 capsules in the morning and 4 capsules in the evening). The first dose of investigational product will be taken in the clinic at Visit 2. All other doses will be taken by the patient in accordance with their normal routine, unless the patient is taking part in the PK sub-study when the morning dose at Visits 4 and 6 should be taken in the clinic after pre-dose assessments. No food should be consumed within the 2 hours prior to the scheduled dose and for one hour after taking the dose.

In the event of an abnormal absolute neutrophil count (ANC) or leucocyte count (according to local laboratory measurements), patients should not take more than 4 doses of investigational product from the time of the abnormal blood test. Patients will be informed that they should not take the morning dose of investigational product 2 days after the first abnormal blood test without first obtaining consent from the clinic that it is appropriate to do so.

The patients will receive a box of medication containing 4 blister packs for the whole treatment period at Visit 2.

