## **12. STATISTICAL METHODS AND SAMPLE SIZE**

### **12.1 Description of analysis sets**

#### **12.1.1 General principles**

The analysis of the data will be based on potentially different subsets according to the purpose of analysis, ie, for safety, PK and PD, respectively. The decision regarding validity of data for inclusion in each of the analysis sets will be based on blind review of the data.

The as-treated principle will be applied to all evaluations; ie, patients who received another treatment than the one assigned in the randomisation list will be analysed as belonging to the actual treatment group and not that assigned by randomisation.

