#### **12.1.3 Safety analysis set**

All patients who are randomised into the study and receive at least one dose of randomised investigational product, AZD5069 or placebo, and for whom any post-dose data are available will be included in the safety analysis set.

Throughout the safety analyses, erroneously treated patients (eg, those randomised to treatment A but actually given treatment B) will be accounted for in the actual treatment group.

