#### **12.1.4 PK analysis set**

The PK analysis set will be based on the safety analysis set. The patients who are in the safety analysis set and provide evaluable PK data appropriate for the evaluation of interest (with no major protocol deviations or violations thought to significantly affect the pharmacokinetics of the drug) will be included in the PK analysis set. It may be that specific data points are not included in this analysis set due to deviations or violations at that specific time. Patients who receive placebo will not be part of the PK analysis set.

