#### **12.1.5 PD analysis set**

The PD analysis set will be based on the safety analysis set. The patients who are in the safety analysis set and provide the evaluable PD data appropriate for the evaluation of interest (with no major protocol deviations or violations thought to significantly affect the PD assessment of the drug) will be included in the PD analysis set. It may be that specific data points are not

included in this analysis set due to deviations or violations at that specific time. Patients who receive placebo will be included in this analysis set.

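### Assay one on-treatment plasma sample per placebo-randomised patient: analyses go by treatment actually received, yet no placebo sample is assayed

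*Protocol*

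**What the plan says.** Plasma for PK is drawn from every randomised patient at Visits 2, 4, 5 and 6 (section 6.6.1), and Table 8 counts these samples for each patient whatever the arm. Section 6.6.2 then limits the assay: "Plasma samples from patients who were dosed with placebo will not be analysed for AZD5069". Section 5.4.2 explains how the laboratory knows which samples are which: "A copy of the randomisation scheme will also be made available to the PK bioanalyst, to enable the analysis of samples from patients who have" (the sentence goes on to say that samples from the active arms are to be put first).

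The analysis rules depend on treatment taken. Section 12.1.1 says that "patients who received another treatment than the one assigned in the randomisation list will be analysed as belonging to the actual treatment group", and section 12.1.3 repeats for the safety set that erroneously treated patients "will be accounted for in the actual treatment group". Placebo patients stay out of the PK set (section 12.1.4: "Patients who receive placebo will not be part of the PK analysis set") but form the control in the PD set (section 12.1.5: "Patients who receive placebo will be included in this analysis set").

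On supply, section 5.5.2 says: "The patients will receive a box of medication containing 4 blister packs for the whole treatment period at Visit 2". No section plans a check assay of any placebo sample.

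**The concern.** An as-treated analysis is only as good as the knowledge of what each patient took. Concentration in plasma is the one objective measure of that in this trial, and under section 6.6.2 it can cast doubt on an active assignment but never on a placebo one. A patient assigned to AZD5069 who received placebo would be below the 1 nmol/L limit of quantification throughout, which is at least a flag. A patient assigned to placebo who took AZD5069 would have no result at all.

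The other safeguards are weaker in that direction. The capsules match in size, weight and colour, and all arms take four per dose (section 5.4.1), so accountability counts show how many capsules were used and not what was in them. Leucocyte results from Visit 2 onward are withheld from the sites, so a neutrophil fall in a placebo patient would not lead the investigator to doubt the kit. One box covers the whole period, so an error in packing or dispensing could last the full 4 weeks.

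At stake is the only control arm in a study whose primary objective is safety. Contamination would make drug and placebo look more alike, which is the unfavourable direction for a safety comparison.

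**Working it through.** **1. The plan's own sample counts.** From section 6.6.1, a main-study patient gives 2 samples × 4 visits = 8, and a sub-study patient gives 5 × 3 extended visits + 2 at Visit 5 = 17. At 4 mL each that is 32 mL and 68 mL. Table 8 gives the same four figures.

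**2. How many samples go unassayed.** Inputs are 60 patients allocated 1:1:1, 16 of them in the sub-study, with the sub-study assumed to split equally over the arms (section 6.6.1 expects this approximately).
- All patients: 44 × 8 + 16 × 17 = 352 + 272 = 624.
- Active arms: (44 × 2/3) × 8 + (16 × 2/3) × 17 = 234.7 + 181.3 = 416.
- Placebo: (44/3) × 8 + (16/3) × 17 = 117.3 + 90.7 = 208, one third of the total.
- Placebo samples after the first dose: (44/3) × 7 + (16/3) × 16 = 188.

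**3. Cost of a minimal check.** One assay per placebo patient is about 20, and 20/416 = 4.8%, about 5% more than the active assays already planned.

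**4. Size of one undetected case.** 1/20 = 5% of the placebo arm. If that patient also had a low-count event, the placebo row would move from 0/20 (exact 95% interval 0 to 16.8%) to 1/20 (0.1 to 24.9%).

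**5. How likely is a case?** The protocol gives no rate. Assuming a per-patient probability q of placebo-to-active misdosing, the chance of at least one case among 20 is 1 − (1 − q)^20:

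| Assumed q | Chance of at least one in 20 |
|---|---|
| 0.5% | 10% |
| 1% | 18% |
| 2% | 33% |
| 5% | 64% |

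**6. How likely is a case that also shows a persistent low count?** Section 3.2.4 expects at most 15% of healthy subjects at 80 mg bd to fall below 1.0 × 10⁹/L for more than 24 hours. With q = 1%, the chance of at least one such event among 20 placebo patients is at most 1 − (1 − 0.01 × 0.15)^20 = 3%. It is about 1.5% if half the errors involve 50 mg and such events at that dose are taken as nil, in line with the expectation there of no neutrophil withdrawals.

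**7. The three rules side by side.** Section 6.6.2 excludes samples by what the patient was dosed with. Section 5.4.2 gives the laboratory only the assigned arm. Section 12.1.1 analyses by actual treatment. For a correctly dosed patient the three agree. For a placebo-randomised patient who took AZD5069 without anyone knowing, the laboratory sees a placebo assignment and leaves the samples unassayed, so the analysis keeps the patient in placebo.

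**The case against.** Several points on the other side are sound.

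- **Wording by treatment taken.** Sections 6.6.2 and 5.4.2 speak of what patients were dosed with or received. A placebo-randomised patient known to have taken AZD5069 is not barred from assay. This stands, but it helps only once the error is known.
- **Assay is not the reclassification rule.** A reader might infer that after a swap of two boxes only the active-assigned patient would be detected and moved, leaving the other in placebo. The documents do not support that: no section makes concentration the basis for actual treatment, values below quantification can also mean non-compliance, and such a finding would probably prompt a kit trace leading to the other box. The silent case is an isolated placebo-to-active error that leaves no mark in the records.
- **Other routes exist.** Assignment runs through IVRS/IWRS, dispensing and returns are accounted for and monitored, and remaining plasma may be stored, so a for-cause assay stays possible. But none is planned, and section 6.6.2 reports further work on stored plasma outside the clinical study report.
- **No rate and no test.** The study is descriptive, so no error rate or power changes, and step 6 shows that a visible distortion of the low-count row is unlikely on modest assumptions. This limits the point to an improvement.
- **An apparent contradiction.** A reader might also take the softer wording of section 5.4.2, which puts active samples first, to conflict with the outright exclusion in section 6.6.2. It is a looseness that changes no result, worth aligning and no more.
- **Detail left elsewhere.** How actual treatment is established may be set out in a plan not shown here. The assay exclusion, however, is fixed in the protocol itself.

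**Conclusion.** The point holds as a cheap improvement. Under the stated rules, assay cannot find a placebo-randomised patient who took AZD5069, and the analysis would then depend on kit or dispensing records to show the error. Each undetected case would be 1 of about 20 placebo patients, 5%, in the safety and neutrophil summaries.

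It would go too far to say that the control arm is contaminated or that the primary safety summaries are unreliable, since the documents give no misdosing rate and the figures in steps 5 and 6 rest on assumed ones. The sample counts assume an equal split of the sub-study. The value of a single check sample assumes that a post-dose concentration on regular dosing would exceed 1 nmol/L; the protocol gives no typical concentrations against which to check this.

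**What to change.** Replace the exclusion in section 6.6.2 with wording such as:

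> For each patient randomised to placebo, one post-dose on-treatment sample from Visits 4 to 6 will be assayed for AZD5069. If AZD5069 is measurable, all samples from that patient will be assayed. The results will be held by the bioanalyst and a designated unblinded person outside the study team, who will reconcile them with kit and dispensing records. Blind-review decisions on evaluability will be made without these results. The actual-treatment assignment will be documented at unblinding, before any summary is produced.

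Align section 5.4.2, so that it says the scheme is used both to identify active samples for full assay and to select the placebo check samples.

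The order of steps matters. Section 12.1.1 bases the analysis sets on blind review, and section 5.4.2 keeps the code unbroken until evaluability decisions are documented, so the check results must not reach those making the blind decisions. The bioanalyst already holds the scheme and needs no further unblinding.

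The cost is about 20 assays on top of about 416 (about 5%), one reconciliation step and a wording change. No extra visit or blood draw is needed.

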## 6.7 Pharmacodynamics

### 6.7.1 Collection of pharmacodynamic markers

#### 6.7.1.1 Circulating neutrophil count

Circulating neutrophil counts (absolute and percentage) will be analysed at local laboratories within 2 hours (maximum 4 hours) of sample collection. Haematology analysis at the central laboratory will include leucocyte (and neutrophil) counts as exploratory variables to be analysed intervals between receipt of sample and 72 hours after sample collection. Samples will be collected, labelled, stored and shipped as detailed the laboratory specifications.

For blood volume see Section 7.1.

#### 6.7.1.2 Biomarker blood sampling

Blood will be taken to generate serum samples for biomarker analysis at Visit 2 (pre-dose) and Visit 6. Analysis will be conducted by a suitably qualified bioanalytical laboratory under guidance of Clinical Pharmacology and DMPK (CPD) or Translation Science (TS) at

AstraZeneca R&D. Samples will be collected, labelled, stored and shipped as detailed in the Laboratory Manual.

### **6.7.1.3 Archive sample**

Blood will be taken to retain a serum sample for future retrospective analysis of mediators relevant to the mechanism of inflammation in COPD at Visits 2 and 6.

Any results from such analyses will be reported separately from the CSR.

Samples will be collected, labelled, stored and shipped as detailed in the Laboratory Manual.

For blood volume see Section [7.1](#).

## **6.8 Pharmacogenetics**

Please refer to Appendix D. These data will not form part of the CSR.

## **6.9 Health economics (Not applicable)**

Not applicable.

## 7. BIOLOGICAL SAMPLING PROCEDURES

### 7.1 Volume of blood

The total volume of blood that will be drawn from each patient in this study is as follows:

**Table 8** Volume of blood to be drawn from each patient

Assessment		Sample volume (mL)	No. of samples	Total volume (mL)
Safety	Clinical chemistry (including LH and FSH at Visit 1.1)	5	7	35
	Haematology	2	7	14
Leucocyte count		2	12 main study (13 PK sub-study)	24 (26 PK sub-study)
Pharmacokinetic		4	8 main study (17 PK sub-study)	32 (68 PK sub-study)
Biomarker blood sample		8.5	2	17
Archive sample		8.5	2	17
Pharmacogenetic		9	1	9
Total				148 (186 PK sub-study)

A cannula will be supplied for repeated samples as required and a small volume will be discarded before each sample is taken.

### 7.2 Handling, storage and destruction of biological samples

The samples will be used up or disposed of after analyses or retained for further use as described here.

Biological samples for future research will be retained at AstraZeneca R&D or delegated facility on behalf of AstraZeneca for a maximum of 15 years following the Last Patient's Last Visit in the study. The results from future analysis will not be reported in the Clinical Study Report but separately in a Scientific Report.

#### 7.2.1 Safety and/or circulating neutrophil samples

The clinical chemistry, haematology, circulating leucocyte (including neutrophil) count and urinalysis samples will be used up during analysis or disposed of after analysis.

### 7.2.2 Pharmacokinetic samples

Samples will be disposed of after the clinical study report has been finalised, unless retained for future analyses, see below.

Key samples for investigation of long-term stability and/or metabolite identification and/or analysis will be retained at AstraZeneca R&D on behalf of Clinical Pharmacology and DMPK(CPD), AstraZeneca for a maximum of 1 year following the finalisation of the Clinical Study Report. The results from the investigation will not be reported in the clinical study report but separately in a bioanalytical/metabolism report.

### 7.2.3 Pharmacodynamic samples

CRP and SAA samples will be disposed of after the clinical study report has been finalised. All other exploratory biomarker samples, including archive biomarker samples, will be held for up to 15 years after last patient last visit; after this time all samples will be destroyed.

### 7.2.4 Pharmacogenetic samples

Please refer to Appendix D.

## 7.3 Labelling and shipment of biohazard samples

The Principal Investigator ensures that samples are labelled and shipped in accordance with the Laboratory Manual and the Biological Substance, Category B Regulations (materials containing or suspected to contain infectious substances that do not meet Category A criteria), see Appendix C 'IATA 6.2 Guidance Document'.

Any samples identified as Infectious Category A materials are not shipped and no further samples will be taken from the patient unless agreed with AstraZeneca and appropriate labelling, shipment and containment provisions are approved.

## 7.4 Chain of custody of biological samples

A full chain of custody is maintained for all samples throughout their lifecycle.

The Principal Investigator at each centre keeps full traceability of collected biological samples from the patients while in storage at the centre until shipment or disposal (where appropriate) and keeps documentation of receipt of arrival.

The sample receiver keeps full traceability of the samples while in storage and during use until used or disposed of or until further shipment and keeps documentation of receipt of arrival.

AstraZeneca keeps oversight of the entire life cycle through internal procedures, monitoring of study sites and auditing of external laboratory providers.

Samples retained for further use are registered in the AstraZeneca biobank system during the entire life cycle.

## 7.5 Withdrawal of informed consent for donated biological samples

If a patient withdraws consent to the use of donated biological samples, the samples will be disposed of/destroyed, and the action documented. If samples are already analysed, AstraZeneca is not obliged to destroy the results of this research.

As collection of the biological samples is an integral part of the study, then the patient is withdrawn from further study participation.

The Principal Investigator:

- Ensures patients' withdrawal of informed consent to the use of donated samples is notified immediately to AstraZeneca
- Ensures that biological samples from that patient, if stored at the study site, are immediately identified, disposed of /destroyed, and the action documented
- Ensures the laboratory(ies) holding the samples is/are informed about the withdrawn consent immediately and that samples are disposed/destroyed, the action documented and the signed document returned to the study site
- Ensures that the patient and AstraZeneca are informed about the sample disposal.

AstraZeneca ensures the central laboratory(ies) holding the samples is/are informed about the withdrawn consent immediately and that samples are disposed of/destroyed and the action documented and returned to the study site.

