## 2. STUDY OBJECTIVES

### 2.1 Primary objective

The primary objective is to evaluate the safety and tolerability of AZD5069 in patients with COPD. The associated primary outcome variables are shown in [Table 1](#).

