## 3. GENETIC RESEARCH PLAN AND PROCEDURES

### 3.1 Selection of genetic research population

#### 3.1.1 Study selection record

All patients will be asked to participate in this genetic research. Participation is voluntary and if a patient declines to participate there will be no penalty or loss of benefit. The patient will not be excluded from any aspect of the main study.

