### 3.1.4 Discontinuation of patients from this genetic research

Specific reasons for discontinuing a patient from this genetic research are:

Withdrawal of consent for genetic research: Patients may withdraw from this genetic research at any time, independent of any decision concerning participation in other aspects of the main study. Voluntary discontinuation will not prejudice further treatment. Procedures for discontinuation are outlined in Section 7.5 of the main Clinical Study Protocol.

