### 4.1 Informed consent

The genetic component of this study is optional and the patient may participate in other components of the main study without participating in the genetic component. To participate in the genetic component of the study the patient must sign and date both the consent form for the main study and the genetic component of the study. Copies of both signed and dated consent forms must be given to the patient and the original filed at the study centre. The principal investigator(s) is responsible for ensuring that consent is given freely and that the patient understands that they may freely discontinue from the genetic aspect of the study at any time.

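### Appendix D makes leaving the optional genetic research independent of the main study, but the procedure it cites, Section 7.5, withdraws the patient from the study and has no exception for the genetic sample

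*Protocol*

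**What the plan says.** Protocol Section 7.5 opens with its trigger: "If a patient withdraws consent to the use of donated biological samples, the samples will be disposed of/destroyed, and the action documented". The trigger is not limited by type of sample. The next paragraph gives the consequence for the patient: "As collection of the biological samples is an integral part of the study, then the patient is withdrawn from further study participation". The rest of the section lists who must be notified and how destruction is documented.

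Appendix D covers the genetic research. Its Section 3.1.4 grants a separate right to leave: "Patients may withdraw from this genetic research at any time, independent of any decision concerning participation in other aspects of the main study". The same paragraph ends: "Procedures for discontinuation are outlined in Section 7.5 of the main Clinical Study Protocol". Appendix D 4.1 confirms that the component is optional, so that "the patient may participate in other components of the main study without participating in the genetic component". Appendix D 3.1.1 says of a patient who declines: "The patient will not be excluded from any aspect of the main study".

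Section 2.1 sets the stake: "The primary objective is to evaluate the safety and tolerability of AZD5069 in patients with COPD".

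**The concern.** The appendix promises one thing and its cross-reference delivers another. A site handling a patient who wants only the DNA sample destroyed is sent by number to a section that takes the patient out of the trial.

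Two things would be at stake. The first is follow-up: a patient with no safety reason to stop would come off product and miss later scheduled laboratory, leucocyte, ECG, vital-sign and spirometry assessments, which are the primary outcome variables in Table 1. The second is the consent position: a right described as independent would cost the patient their place in the trial, and this might discourage its use.

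**Working it through.** No figure in the protocol is in dispute and no formal sample size calculation was made (Section 12.3), so the check is mainly a comparison of texts.

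**Step 1: does Section 7.5 reach the genetic sample?** Its trigger covers donated samples without distinction, and neither Section 7.5 nor Appendix D carves out the DNA sample. Appendix D 3.1.4 cites Section 7.5 specifically for people leaving the genetic research. The protocol therefore applies Section 7.5 to them itself.

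**Step 2: is another procedure available?** Section 7.2.4 sends pharmacogenetic samples to Appendix D. Section 5.8 sends the reasons for stopping the genetic research there too. Appendix D then returns the reader to Section 7.5. Appendix D 3.3 mentions tracing samples for destruction when consent is withdrawn, but says nothing about the patient's status in the study. Nothing breaks the circle.

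**Step 3: when would it happen?** Appendix D 3.2 takes the sample at Visit 2 after randomisation, or at a later visit. A change of mind during the study therefore falls in the treatment or follow-up period.

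**Step 4: what would be lost?**

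| Item | Source | Result for this patient |
|---|---|---|
| Product and assessments | Section 5.9 | Withdrawal from study covers both |
| Replacement | Sections 5.2.1 and 5.9 | None |
| Data already collected | Section 12.2.1 | Kept up to discontinuation |
| Adverse events | Sections 5.9 and 6.4.3 | Patient asked about them, seen by an investigator if possible, and events followed up |
| Missing later values | Section 12.2.1 | Not handled unless specified |

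The loss is the scheduled assessments after the withdrawal date, not the patient's whole safety record.

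**Step 5: scale.** Per arm, 60/3 = 20, which agrees with the synopsis. One patient is 1/20 = 5% of an arm. As an upper bound, suppose one patient's follow-up were lost entirely. The chance of seeing at least one event in an arm is 1 − (1 − p)^n, where p is an assumed event rate:

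| Assumed p | n = 20 | n = 19 | Drop |
|---|---|---|---|
| 5% | 1 − 0.95^20 = 64.2% | 1 − 0.95^19 = 62.3% | 1.9 points |
| 10% | 1 − 0.90^20 = 87.8% | 1 − 0.90^19 = 86.5% | 1.3 points |
| 15% | 1 − 0.85^20 = 96.1% | 1 − 0.85^19 = 95.4% | 0.7 points |

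The event rates are assumptions, not protocol figures. The true effect of one such patient would be smaller than these drops, because Step 4 shows that earlier data and adverse event follow-up are retained.

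**The case against.** The best defence is that the withdrawal sentence carries its own reason: sample collection is integral to the study. That reason does not fit a component the protocol calls optional and for which it takes separate consent. A site must also read the independence sentence in Appendix D 3.1.4 before it reaches the reference to Section 7.5. A sensible reader could then take only the notification and destruction steps from Section 7.5.

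This reading is available and may well be what was intended. It shows that a wrong withdrawal is possible rather than certain. It does not remove the conflict, because the exclusion is only implied, while the reference to Section 7.5 is explicit and unqualified.

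A reader might also infer more than the documents support:

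- **That the same fault affects archive serum and stored spare plasma.** No passage calls these optional. Table 3 and Section 6.7.1.3 schedule the archive sample for all patients, Table 8 counts it in the blood volume, and Section 2.3 lists both storage aims among the exploratory objectives. Treating them as integral is consistent with Section 7.5. A different consent policy would be a preference, not a correction.
- **That adverse event collection stops.** Section 5.9 says otherwise.
- **That the assurance in Appendix D 3.1.1 is broken.** That wording concerns a patient who declines at the outset. The direct conflict is with the independence sentence in 3.1.4.
- **That a particular number of patients would be lost.** Appendix D 6 says that even the number joining the genetic research is unknown, so no count can be given.

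**Conclusion.** The inconsistency is real and rests on the wording alone: Appendix D 3.1.4 and Section 7.5 cannot both be followed literally when a patient leaves only the genetic research. The effect on the trial's results is minor. It requires a patient to consent to the DNA sample, give it, revoke only that consent while still in the study, and be at a site that applies Section 7.5 in full. The frequency is unknown and probably small, and each case would cost about 5% of one arm its remaining scheduled assessments. No hypothesis test depends on it. The point is low in severity but worth correcting, because the text as it stands can produce the opposite of what Appendix D promises the patient.

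**What to change.** Make two short edits:

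1. In Section 7.5, state that the sentence ending study participation does not apply when consent is withdrawn only for the optional genetic sample. In that case the sample is destroyed, the destruction is documented, and the patient's main-study participation is unaffected.
2. In Appendix D 3.1.4, limit the reference to the notification and sample-destruction steps of Section 7.5.

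If the consent forms repeat the Section 7.5 wording, they need the matching change; those forms were not available here. No visit, dose, sample or analysis changes. The cost is about one clause in each place, plus whatever approval Section 8.5 requires for the amendment.
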